### **10.4 Competent Authorities**

Notification to local authorities are needed for this PASS survey.

## **11 Management and Reporting of Adverse Events/Adverse Drug Reactions**

This study is not designed to capture safety events associated with the use of isatuximab

## **12 Plans for Disseminating and Communicating Study Results**

### **12.1 Overview**

Sanofi will monitor the data collected while the study is being conducted and consider their implications for the effectiveness of the isatuximab educational materials.

Any new information about the minimisation of the risk of interference for blood typing (minor antigen) (positive indirect Coombs' test) will be evaluated for a potential study protocol amendment.

### **12.2 Study Report**

Upon completion of the study, a study report will be prepared by Sanofi and Evidera.

The study report will be sent to the EMA in accordance with the guidelines and the study results will also be presented in the *Periodic Safety Update Report* (PSUR) and in the *Risk Management Plan*, as applicable.

### **12.3 Data Ownership**

The data collected in this study are the property of Sanofi.

Copying or spreading information related to this study without Sanofi's agreement is prohibited.

### **12.4 Publications**

Study findings will be published in a peer reviewed journal.

Any publication will be guided by the Uniform Requirements for Manuscripts Submitted to Biomedical Journals: Writing and Editing for Biomedical Publication of the International Committee of Medical Journal Editors (ICMJE), updated April 2010.

[figure not shown]
All reporting will be consistent with the STROBE (Strengthening the Reporting of Observational studies in Epidemiology) Initiative checklist for cohort studies (STROBE 2008).

Still in line with the EMA guideline, and in order to allow competent authorities to review in advance the results and interpretations to be published, the MAHs should communicate to the Agency and the competent authorities of the Member States in which the product is authorised the final manuscript of the article within two weeks after first acceptance for publication.

## **Appendix A. Isatuximab Brochure**

IMPORTANT INFORMATION

**SARCLISA (ISATUXIMAB)  
IS ASSOCIATED WITH RISK  
OF INTERFERENCE FOR BLOOD TYPING**

[figure not shown]
[figure not shown]
[figure not shown]
**HEALTHCARE PROFESSIONALS  
AND BLOOD BANKS BROCHURE**

HCPs Leaflet: version 12 MAR 2021

## WARNING FOR BLOOD BANKS

- Isatuximab is bound to CD38 on red blood cells (RBCs) and may mask the detection of antibodies to minor antigens in the patient's serum. Thus, isatuximab may interfere with routine blood compatibility tests with **potential false positive reactions in indirect antiglobulin tests (indirect Coombs tests)**.
- This interference is limited to the minor blood groups and does not affect the determination of a patient's ABO and Rh blood type.
- Isatuximab interference mitigation methods include treating reagent RBCs with dithiothreitol (DTT) to disrupt isatuximab binding or other locally validated methods. Since the Kell Blood group system is also sensitive to DTT treatment, Kell-negative units should be supplied after ruling out or identifying alloantibodies using DTT-treated RBCs.
- If an emergency transfusion is required, you can give non-cross-matched ABO/Rh-compatible RBCs as per local blood bank practices.

ISA = Isatuximab    Y = Coombs reagent    ● = CD38 receptor    ● = Red Blood Cells    Y = Antibodies to minor antigen

## WARNING FOR HEALTHCARE PROFESSIONALS

### APPROPRIATE MEASURES TO MANAGE ISATUXIMAB INTERFERENCE AND AVOID POSSIBLE RESULTING ADVERSE CLINICAL CONSEQUENCES

- Conduct blood type and screen tests on your patient prior to the first infusion of isatuximab.
- Consider phenotyping prior to starting isatuximab treatment as per local practice.
- Give your patient the latest version of the **Patient Card**.
- If treatment with isatuximab has already started, inform the blood bank that the patient is receiving isatuximab.
- In the event of a planned transfusion, please notify blood transfusion centers about the risk of interference with indirect antiglobulin tests.
- There is currently no available information with regards to how long the interference with the indirect Coombs test may persist after the last infusion of isatuximab. Based on the half-life of isatuximab, it is anticipated that isatuximab mediated positive indirect Coombs test may persist for approximately **6 months** after the last infusion. Therefore, please advise your patient to carry the Patient Card at all times and until 6 months after the last dose of isatuximab.
- It is important you always advise your patient to consult the Package Leaflet (PL) for further information on isatuximab.

### REPORTING OF SUSPECTED ADVERSE REACTIONS

Isatuximab is subject to additional monitoring of its benefit/risk balance. This will allow quick identification of new safety information. Healthcare professionals are asked to report any suspected adverse reactions via the national reporting system at the following:

- **[TELEPHONE NUMBER OF LOCAL MEMBER STATE NATIONAL COMPETENT AUTHORITY]**
- Or **[ADDRESS OF LOCAL MEMBER STATE NATIONAL COMPETENT AUTHORITY]**

### ADDITIONAL RESOURCES

For additional information on isatuximab, **please refer to the Summary of Product Characteristics (SmPC)** or contact SANOFI by using one of the following methods:

- **Phone: [TO BE COMPLETED DURING LOCAL ADAPTATION]**
- **Email: [TO BE COMPLETED DURING LOCAL ADAPTATION]**
- **Website: [TO BE COMPLETED DURING LOCAL ADAPTATION]**

## FOR TIMELY TRANSFUSIONS

### REMINDER FOR HEALTHCARE PROFESSIONALS

- Conduct blood type and screen tests on your patient prior to the first infusion of isatuximab. Inform the blood bank that your patient has been treated with isatuximab which may interfere with indirect antiglobulin tests (indirect coombs tests).

- Verify standing orders for transfusions to determine if your patient received isatuximab within the last year.

- In the event of a planned transfusion, notify blood transfusion centers about the risk of interference with indirect antiglobulin tests.

- Give your patient a Patient Card to be carried at all times and until **6 months** after the last dose of isatuximab. Provide your patient's pre-isatuximab compatibility profile, if available, to the blood bank.

- Ask your patient to tell their other healthcare professionals that they have received isatuximab, particularly before a transfusion, and to show them their Patient Card.

### REMINDER FOR BLOOD BANKS

- Identify the blood sample of your patient as containing isatuximab.

## **Appendix B. Patient Card**

## MY INFORMATION

Patient's name:

Patient's date of birth  
(DD / MMM / YYYY):

Patient's phone:

Emergency contact  
(name):

Emergency contact  
(phone):

## MY TREATMENT DETAILS

Please complete this section  
or ask your doctor to do it.

Isatuximab recommended dose  
of 10 mg/kg and dosing schedule:

**Cycle 1:** Days 1, 8,  
15 & 22 (weekly)

**Start date**  
(DD / MMM / YYYY):

**End date**

(DD / MMM / YYYY):

**Cycle 2 and beyond:**  
Days 1 & 15 (every  
2 weeks)

## MY BLOOD RESULTS

Before starting isatuximab, the results  
of my blood test collected on:

were:

Blood type:  A  B  AB  O  Rh+  Rh-

The result of my indirect antiglobulin test (indirect Coombs test) was:

Negative

Positive for the following antibodies:

## MY DOCTOR'S INFORMATION

[figure not shown]
In case of emergency, or if you find this card,  
please contact my doctor using the details below.

Doctor's name:

Doctor's phone:

Patient Card: Version 21 MAR 2021

SANOFI 

  
**SARCLISA**®  
(isatuximab)

## PATIENT CARD

### — DEAR PATIENT RECEIVING SARCLISA (ISATUXIMAB) —

- Provide this card to healthcare providers **before** blood transfusion.
- Keep this card with you at all times and until **6 months** after the last dose of isatuximab.
- This medicine is subject to additional monitoring. This will allow for the identification of new safety information. You can help by reporting any side effects you may get. If you notice any side effects, talk to your doctor or pharmacist. You can also report side effects directly at **www.xxx.xxx**. Side effects should also be reported to SANOFI on **Tel: xxxxxxxxxxxx**. By reporting side effects, you can help provide more information on the safety of this medicine.
- For further information on isatuximab, you can consult the **Package Leaflet (PL)**.

### — WARNING FOR HEALTHCARE PROVIDERS —

- Please note this patient is receiving treatment with **SARCLISA (isatuximab)**.
- This patient card contains important safety information that you need to be aware of before, during, and after treatment with isatuximab.
- Treatment with isatuximab binds to CD38 on red blood cells (RBCs) and is associated with a **Risk of Interference with blood typing (positive indirect Coombs Test)**, which may persist for approximately 6 months after the last isatuximab infusion.
- To avoid potential problems with RBC transfusion, you should perform blood type and screen tests prior to the first infusion of isatuximab. **Phenotyping may be considered as per local practice.**
- If treatment with isatuximab has already started and in the **event of a planned transfusion, you should notify** the blood bank that the patient is receiving isatuximab and its **risk of Interference with Indirect Antiglobulin Tests**.
- For additional information on isatuximab, please refer to the **Summary of Product Characteristics (SmPC)**.

---

## Appendix C. Survey Questionnaire

### HCP Characteristics and Screening Questions

**P0.** Our records show that your practice is in [insert country from contact information]. Is this correct?

1. Yes
2. No

PI – List Drop Down.

[DP:1]

**P0a.** Please select the country where you practice.

PI- show if P0=2

PI – List Drop Down.

[DP:1]

**P1.** Our records show that your primary specialty is [insert specialty]. Is this correct?

1. Yes
2. No

PI – List Drop Down.

[DP:1]

**P1a** What is your primary medical specialty?

- Medical oncology
- Haemato-oncology/onco-haematology
- Internal medicine
- Blood banking transfusion medicine
- Other, specify \_\_\_\_\_

PI- show if P1=2

PI – List Drop Down.

[DP:1]

**P1b.** Please select your sub-specialty from the following list

Medical Oncology subspecialties:

- Hematology Oncology
- Surgical Oncology
- Pediatric Hematology Oncology
- Blood bank transfusion medicine?
- Other specify\_\_\_\_\_

Hematology subspecialties:

- Bone marrow stem cell transplantation
- Blood bank transfusion medicine?
- Other specify\_\_\_\_\_

**Internal medicine subspecialties:**

- Vascular Medicine
- Medical Oncology
- Intensive Care
- Other specify \_\_\_\_\_

**PI – List Drop Down.**

PI- Drop down with list of subspecialties; show Medical Oncology subspecialties if P1a= Medical Oncology; show Hematology subspecialties if P1a= Haemato-oncology/onco-haematology; show Internal medicine subspecialties if P1a= Internal medicine

[DP:1]

-----Page Break-----

**Px.** For the treatment of Multiple Myeloma, please indicate your level of adoption of **isatuximab**.

- Prescribe on a regular basis
- Have prescribed at least once
- Are aware but have never prescribed
- Are not aware

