### Inclusion Criteria

- The HCP is involved in the management and follow-up of multiple myeloma, such as oncology/haematology specialists and HCPs associated with blood banks/transfusion centres who have not necessarily prescribed isatuximab.
  - Prescribers (Oncologists/Haematologists): The HCP has prescribed isatuximab at least once.
  - Non-prescribers (Blood banks/transfusion centres): The HCP has provided blood products at least once for a patient treated with isatuximab.
- The HCP provides consent to participate.

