To minimise selection bias, the number of HCPs is targeted based on the combination of the country population, target population (haematology and haemato-oncology centres and blood banks), and date of distribution of educational materials. Since this survey is targeting HCPs instead of patients, this recruitment approach will reflect the proportion of HCP prescribers/non-prescribers within these countries. Approximately 400 HCPs will be included in this study. It is expected that the European Union countries with a large population will have a greater number of HCPs included in the study compared to countries with a smaller population. In addition, the number of HCPs included per country will vary based on the volume of distribution of educational materials for each country. Recruitment strategy for HCPs will vary among countries as the aim will be to recruit HCPs who properly represent the HCP specialities and practice settings where educational materials are distributed in each country. Additional factors that will be considered during recruitment, in efforts for representativeness, include recruiting HCPs from different regions in each country, and recruiting HCPs with varying numbers of patients treated with isatuximab.

The final response rate is estimated to be 4.4%-6.8% based on historical LiveTracker™ data (17% of HCPs will respond to communication emails, and of those who respond, approximately 26% to 40% will be eligible and will complete the survey). In order to obtain close to 400 completed questionnaires, a total of approximately 6,000 to 9,000 invitation emails will be sent (it varies among country and will be adjusted based on the response rates of each country and each types of HCPs).

These invitation emails are planned to be sent using a stratified random sampling method, however, further random sampling steps after the initial email is likely not feasible since the goal is to maximize responses. A few reasons it is not feasible include 1) the low numbers of HCPs in some countries; 2) the low expected response rate (4.4%-6.8%).

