### 9.6.1 Data Collection

Data for this study will be collected electronically by Evidera, the owner of LiveTracker™ platform. LiveTracker™ is a cloud-based, real-time, continuous electronic data collection platform that delivers real-world evidence data. LiveTracker™ has the capability to perform automatic checks of data quality and missing-ness. The administration of measures will be conducted according to the protocol.

---

Once HCPs click on their unique online data collection form link, they will be tracked through a unique identifier within the LiveTracker™ platform. The HCP will be asked to complete the self-reported items. The questionnaire is assumed to take approximately 15 minutes to complete. Each HCP has ultimate responsibility for the self-reporting of all data entered in the LiveTracker™, and ensuring that they are accurate, complete, consistent, legible and timely (contemporaneous).

HCPs who delay in completing the survey or who do not complete all contents of the survey in a session will be encouraged to complete their forms through e-mail and/or phone reminders. Any queries to the HCPs will be monitored until resolution within the LiveTracker™ platform through the electronic query report. The survey is considered valid if all questions are completed.

A small amount of incentive payment (country-specific fair market value payments based on physician contracts through the LiveTracker™ Panel, as allowed per the local law and regulations) will be made to HCPs as a compensation for the time spent to complete the questionnaire (about 15 minutes).

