**PI – List Drop Down**

[DP:1]

**Px1.** Please select if your primary setting at the office, clinic or hospital is one of the below

- Blood bank
- Transfusion centre
- Blood donation centre
- None of the above

PI- show if Px0= Private office/ Clinic, Academic/ University hospital, District General/ Community / Non-Teaching Public Hospital, Private hospital

**Px2.** Have you provided blood products to a Multiple Myeloma patient treated with **isatuximab**?

- Provided blood products on a regular basis
- Provided blood products at least once

- Have never provided blood products

PI- List drop down

[DP:1]

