**Screening criteria: Screen-in if**

- “Prescribe on a regular basis” or “at least once” on question Px
- OR**
- “Provided blood products on a regular basis” or “at least once” on question Px2.

-----Page Break-----

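### The paid survey screens on questions that name only isatuximab, so the qualifying answer is easy to guess, and the questionnaire contains no later check on eligibility

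*Protocol*

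**What the plan says.** Section 9.2.2 defines a prescriber by "The HCP has prescribed isatuximab at least once" and a non-prescriber by "The HCP has provided blood products at least once for a patient treated with isatuximab".

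Appendix C puts these criteria into practice through one item each. Px reads "For the treatment of Multiple Myeloma, please indicate your level of adoption of" isatuximab and offers four levels, of which the upper two are positive. Px2 reads "Have you provided blood products to a Multiple Myeloma patient treated with" isatuximab and offers three levels, of which two are positive. The screening rule admits anyone with a positive answer to either item. As printed, Px2 carries no display condition, and the rule adds no requirement on practice setting.

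Section 9.2.3 says that the invitation e-mail explains the study objective and carries the survey link. It expects 17% of invited HCPs to respond and says that "of those who respond, approximately 26% to 40% will be eligible and will complete the survey". Section 9.6.1 says that a small payment "will be made to HCPs as a compensation for the time spent to complete the questionnaire". Section 9.9 accepts that the self-reported data cannot be objectively verified and that respondents will not be contacted to clarify their answers.

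Section 9.3.1 lists two items to be collected in the questionnaire to assess the selection criteria: the number of patients prescribed isatuximab in the past year, and the time since the last such prescription. Neither item appears in Appendix C.

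**The concern.** A panel member who has been told what the study is about, and who is then asked about a single product, can see which answer leads to the paid questionnaire. Most responders are expected not to become eligible completers, so a modest false-positive rate among them is magnified relative to the true users.

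The three success criteria in section 9.7.4 are computed on whoever passes this screen and are compared with a fixed 80%. HCPs who never used the product, or never supplied blood to a treated patient, would dilute those proportions. Without the section 9.3.1 items, the analyst has nothing in the questionnaire with which to identify them afterwards.

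**Working it through.** **Inputs.** From section 9.2.3: 6,000 to 9,000 invitations, 17% responding, and 26% to 40% of responders eligible and completing. From Table 3: 40 to 100 non-prescribers. Assumed, because the protocol gives no figure: an over-claim rate f of 2%, 5% or 10%.

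**The plan's own figures.** 0.17 × 0.26 = 4.4% and 0.17 × 0.40 = 6.8%, as stated. For 400 completed questionnaires, 400/0.068 = 5,882 and 400/0.0442 = 9,050 invitations, which agrees with 6,000 to 9,000.

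**Responders who are not eligible completers.**
- 6,000 invitations at 40%: 1,020 responders, 408 eligible completers, 612 others.
- 9,000 invitations at 26%: 1,530 responders, 398 eligible completers, 1,132 others.

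This is 612/408 = 1.5 to 1,132/398 = 2.8 others per eligible completer.

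**Ineligible share of the sample.** With e the eligible-and-completing fraction and h the fraction of the others who are non-users, share = f·h·(1−e) / [e + f·h·(1−e)]. The ranges run from e = 40% to e = 26%.

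| f (assumed) | all others are non-users (h = 1) | half are non-users (h = 0.5) |
|---|---|---|
| 2% | 2.9% to 5.4% | 1.5% to 2.8% |
| 5% | 7.0% to 12.5% | 3.6% to 6.6% |
| 10% | 13.0% to 22.2% | 7.0% to 12.5% |

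Example: f = 5%, e = 0.26, h = 1 gives 0.05 × 0.74 = 0.037, and 0.037/(0.26 + 0.037) = 12.5%.

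**If the 26-40% already contains over-claimers.** Call that observed fraction q. The true fraction is then t = (q − f)/(1 − f) and the share is f(1 − t)/q. This gives 7.9% to 15.0% at f = 5% and 16.7% to 31.6% at f = 10%.

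**Rate needed for a 10% share (h = 1).** f = 0.1e/[0.9(1 − e)], which is 3.9% at e = 26% and 7.4% at e = 40%.

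**Effect on a proportion.** If ineligible HCPs scored 20 points lower (assumption), the shift is share × 20: 0.6 points at a 3% share, 1.4 at 7%, 2.5 at 12.5% and 4.4 at 22.2%. For comparison, the 95% half-width at 80% with n = 400 is 1.96 × √(0.8 × 0.2/400) = 3.9 points.

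**Non-prescribers.** With 40 respondents, four over-claimers are 10% of the group. As printed, an HCP who fails Px can still be asked Px2. Both section 9.3.1 items concern prescribing, so even if restored they would not check this group.

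**The case against.** The strongest reply has five parts.

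- **The size rests on an assumed rate.** This stands. At 2% the share is only 3-5%, and nothing in the protocol supports 5% or 10% over any other value. A reader might infer that the sample will contain a sizeable ineligible share; the documents do not show that.
- **The 60-74% remainder is not all non-users.** This stands. Section 9.2.3 gives one combined figure for eligibility and completion, so the remainder includes eligible HCPs who did not finish. The half-and-half column allows for this. An over-claimer must also answer every question to count as valid (section 9.6.1).
- **Over-claimers were not necessarily outside the audience.** This stands. A reader might infer that they lower the receipt rate because the materials were never meant for them. Table 1 shows distribution by specialty, for example 2,002 haematologists and 778 oncologists in France, so a non-user may well have been a recipient. An effect on the receipt rate is not shown.
- **The bias is small and conservative.** This stands in part. At shares of 3% to 12.5% the illustrated shift lies within sampling error, and less knowledgeable respondents would make 80% harder to reach. The direction is not assured for every item, however: the key question is true/false with true correct, so a guesser can pass it.
- **There are safeguards and a disclosed limitation.** This stands in part. Panel members pass a credentials check and are profiled on specialty and caseload (section 9.2.3), but isatuximab use is not among the profile items named. Section 9.9 discloses self-report in general and places no safeguard on eligibility.

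**Conclusion.** The point holds as a weakness of the instrument, of uncertain size. Both screening items name only the qualifying product, completion is paid, the objective is explained beforehand, and the items planned for assessing the selection criteria are absent from the questionnaire. That the invitation itself names isatuximab is an inference from the study objective, since its text is not in the protocol.

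The magnitude is conditional throughout. The contamination is minor at 2% over-claiming. It becomes material at 5% to 10%, where it is roughly halved if half of the remaining responders are eligible non-completers. The expected consequence is some dilution of the knowledge and behaviour proportions, mattering most when a result lies near 80% and in the small non-prescriber group. Because answers are neither verified nor queried afterwards, prevention before fieldwork is worth its small cost.

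**What to change.** 1. Ask Px as a grid over several myeloma treatments with the same four levels, isatuximab being one row. Ask Px2 as a list of treatments received by patients who were given blood products. Screen in on the isatuximab entry only, so the eligibility criteria do not change.
2. Word the section 9.2.3 invitation and the information shown before screening generically (myeloma treatment and transfusion safety), and name the product once the screen is passed. Masking the items achieves little without this step.
3. Add the two section 9.3.1 usage items to Appendix C. Define inconsistency in advance, for example regular prescribing with no patients in the past year, and repeat the main proportions without inconsistent respondents. An HCP whose only prescription is more than a year old is eligible and must not be flagged for that alone.

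The cost is reprogramming the screening items, a revised invitation and pre-screen text cleared before fieldwork, and about a minute more per respondent. For non-prescribers the protection comes from the first two steps alone.
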